**Table 9.2: Solicited systemic reactions: terminology, definitions, and intensity scales**

CRB term (MedDRA LLT)	Fever	Vomiting	Crying abnormal	Drowsiness	Appetite lost	Irritability
Data analysis term (MedDRA preferred term)	Pyrexia	Vomiting	Crying	Somnolence	Decreased appetite	Irritability
Diary card term	Temperature	Vomiting	Abnormal crying	Drowsiness	Loss of appetite	Irritability
Definition	Elevation of temperature to $\geq 38.0^{\circ}\text{C}^*$ ( $\geq 100.4^{\circ}\text{F}$ )	Vomiting does not include spitting up	Inconsolable crying without a determined reason	Reduced interest in surroundings, or increased sleeping	See intensity scale	An excessive response to stimuli: increased fussiness, whining, and fretfulness despite attempts to comfort the infant and despite caregiver responses that would normally be soothing
Intensity scale*	Grade 1: $\geq 38.0^{\circ}\text{C}$ to $< 38.5^{\circ}\text{C}$ or $\geq 100.4^{\circ}\text{F}$ to $< 101.3^{\circ}\text{F}$  Grade 2: $> 38.5^{\circ}\text{C}$ to $< 39.5^{\circ}\text{C}$ or $> 101.3^{\circ}\text{F}$ to $< 103.1^{\circ}\text{F}$  Grade 3: $> 39.5^{\circ}\text{C}$ or $> 103.1^{\circ}\text{F}$	Grade 1: 1 episode per 24 hours  Grade 2: 2–5 episodes per 24 hours  Grade 3: $\geq 6$ episodes per 24 hours or requiring parenteral hydration	Grade 1: $< 1$ hour  Grade 2: 1–3 hours  Grade 3: $> 3$ hours	Grade 1: Sleepier than usual or less interested in surroundings  Grade 2: Not interested in surroundings or did not wake up for a feed / meal  Grade 3: Sleeping most of the time or difficult to wake up	Grade 1: Eating less than normal  Grade 2: Missed 1 or 2 feeds / meals completely  Grade 3: Refuses $\geq 3$ feeds / meals or refuses most feeds / meals	Grade 1: Easily consolable  Grade 2: Requiring increased attention  Grade 3: Inconsolable

\* For the Russian Federation, febrile illness is defined as temperature  $\geq 37^{\circ}\text{C}$ ). A prospective subject should not be included in the study until the condition has resolved or the febrile event has subsided.

† For all reactions but fever, parents / guardians will record the intensity level (Grade 1, 2, or 3) in the diary card. For fever, they will record the body temperature, and the classification as Grade 1, 2, or 3 will be assigned at the time of the statistical analysis based on the unit used to measure the temperature and the intensity scale.

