Definition	Elevation of temperature to $\geq 38.0^{\circ}\text{C}^*$ ($\geq 100.4^{\circ}\text{F}$)	Vomiting does not include spitting up	Inconsolable crying without a determined reason	Reduced interest in surroundings, or increased sleeping	See intensity scale	An excessive response to stimuli: increased fussiness, whining, and fretfulness despite attempts to comfort the infant and despite caregiver responses that would normally be soothing
Intensity scale*	Grade 1: $\geq 38.0^{\circ}\text{C}$ to $< 38.5^{\circ}\text{C}$ or $\geq 100.4^{\circ}\text{F}$ to $< 101.3^{\circ}\text{F}$ Grade 2: $\geq 38.5^{\circ}\text{C}$ to $< 39.5^{\circ}\text{C}$ or $\geq 101.3^{\circ}\text{F}$ to $< 103.1^{\circ}\text{F}$ Grade 3: $\geq 39.5^{\circ}\text{C}$ or $\geq 103.1^{\circ}\text{F}$	Grade 1: 1 episode per 24 hours Grade 2: 2–5 episodes per 24 hours Grade 3: ≥ 6 episodes per 24 hours or requiring parenteral hydration	Grade 1: < 1 hour Grade 2: 1–3 hours Grade 3: > 3 hours	Grade 1: Sleepier than usual or less interested in surroundings Grade 2: Not interested in surroundings or did not wake up for a feed / meal Grade 3: Sleeping most of the time or difficult to wake up	Grade 1: Eating less than normal Grade 2: Missed 1 or 2 feeds / meals completely Grade 3: Refuses ≥ 3 feeds / meals or refuses most feeds / meals	Grade 1: Easily consolable Grade 2: Requiring increased attention Grade 3: Inconsolable

* For the Russian Federation, febrile illness is defined as temperature $\geq 37^{\circ}\text{C}$). A prospective subject should not be included in the study until the condition has resolved or the febrile event has subsided.

† For all reactions but fever, parents / guardians will record the intensity level (Grade 1, 2, or 3) in the diary card. For fever, they will record the body temperature, and the classification as Grade 1, 2, or 3 will be assigned at the time of the statistical analysis based on the unit used to measure the temperature and the intensity scale.

Important notes for the accurate assessment of temperature:

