4.4 Derived Endpoints: Calculation Methods

4.4.1 Safety

4.4.1.1 Solicited Reactions

4.4.1.1.1 Daily Intensity

All daily records for solicited reactions will be derived into daily intensity according to the following classification: None, Grade 1, Grade 2, Grade 3, or Missing (Unknown).

For the derivation of daily intensities, the following sequential steps will be applied:

- 1) Solicited reactions (except Fever/Pyrexia) with CRF presence recorded as "No" and with all daily records missing (Unknown) then all daily intensities will be derived as None.
- 2) For non-measurable solicited reactions, daily intensities will correspond to daily records reported in the clinical database. For measurable solicited reactions the daily measurements reported in the clinical database will be converted based upon the intensity scales defined in the protocol; this assumes a reaction that is too large to measure (non-measurable, "NM") is Grade 3. Note the intensity could be considered "None" (not a reaction) in the analysis despite being considered a reaction by the investigator

Note: The maximum intensity on the ongoing period is derived from the record of the maximum intensity/measurement after the end of the solicited period following the rule described above.

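### SAP 4.4.1.1.1 grades fever on the protocol scale, which as printed has no grade for exactly 38.5 °C or 39.5 °C; the SAP's own table has no such gap

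*SAP*

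**What the plan says.** **When fever is graded.** Parents record a temperature, not a grade. The footnote to the SAP's solicited systemic reaction table says: "For fever, they will record the body temperature, and the classification as Grade 1, 2, or 3 will be assigned" at the time of analysis. Protocol Table 9.2 carries the same footnote.

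**Which scale is cited.** SAP 4.4.1.1.1 (Daily Intensity) says that measurable reactions "will be converted based upon the intensity scales defined in the protocol". The permitted results are None, Grade 1, Grade 2, Grade 3 or Missing.

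**Protocol Table 9.2.** The Celsius bounds for fever are "Grade 1: $\geq 38.0^{\circ}\text{C}$ to $< 38.5^{\circ}\text{C", then "Grade 2: $> 38.5^{\circ}\text{C}$ to $< 39.5^{\circ}\text{C", then "Grade 3: $> 39.5^{\circ}\text{C". The Fahrenheit bounds follow the same pattern at 101.3 and 103.1. The definition row sets fever at 38.0 °C or more.

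**The SAP's own table** (captioned 4.4, but called Table 4.2 in the list of tables and in the sentence introducing it). Grade 1 is the same. The next two grades read "Grade 2: $\geq 38.5^{\circ}\text{C}$ to $< 39.5^{\circ}\text{C" and "Grade 3: $\geq 39.5^{\circ}\text{C", with matching Fahrenheit bounds.

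**Downstream use.** SAP 4.4.1.1.2 takes the maximum daily intensity over the period, and 4.4.1.1.3 decides from that maximum whether the reaction was present.

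**Declared changes.** SAP 5.7 records a two-step analysis and the measles cutoff correction from 225 to 255 mIU/mL. It does not mention the fever boundaries.

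**The concern.** The derivation rule sends the programmer to one scale while the SAP prints a different one, and the two disagree at the points where a grade changes. Because no grade is collected from the parent, nothing in the database fills the gap.

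Fever and its grade feed the solicited-reaction summaries for all four groups. If the protocol scale were coded as printed, any error would run one way: a boundary reading would lose its grade and could never gain a higher one. SAP 4.4.1.1.1 gives no rule for a valid temperature that matches no grade. It also warns that the analysis may show None where the investigator saw a reaction, so an ungraded boundary fever might not look like a programming error. The scale is reused for unsolicited fever (protocol 9.3.2.3.3), and there the cross-references in SAP 4.4.1.2.2 are broken.

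**Working it through.** The plan states no figure to reproduce, so the check applies both scales as printed.

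**Inputs.** The bounds come from protocol Table 9.2 and the SAP's systemic-reaction table. Readings are assumed to be recorded to 0.1 degree, since the documents do not state the thermometers' resolution.

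**The Fahrenheit gaps are the same points.** 38.5 × 1.8 + 32 = 101.3 and 39.5 × 1.8 + 32 = 103.1.

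**Enumeration.** Each scale was applied to every reading from 38.0 to 41.0 °C (31 readings) and from 100.4 to 105.8 °F (55 readings).

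| Reading | Protocol Table 9.2 | SAP table |
|---|---|---|
| 38.5 °C / 101.3 °F | no grade | Grade 2 |
| 39.5 °C / 103.1 °F | no grade | Grade 3 |
| all others in range | exactly one grade | the same grade |

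The protocol scale leaves two readings ungraded in each unit. The SAP table leaves none. The scales differ nowhere else.

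**Consequence under SAP 4.4.1.1.2 and 4.4.1.1.3, if the protocol scale is coded literally:**

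- Peak 39.5 °C with another day at 39.0 °C: the maximum is Grade 2, where the SAP table gives Grade 3.
- Peak 38.5 °C with another day at 38.2 °C: the maximum is Grade 1, where the SAP table gives Grade 2.
- Only febrile day 38.5 °C, other days below 38.0 °C: no graded day remains, so the child could be counted as not febrile.
- Only recorded day 38.5 °C: if that day is treated as missing, presence is missing and the child leaves the fever denominator.

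**Effect of one misclassified child.** With planned enrolment and complete data, one child moves the group's percentage by 1/200 = 0.5 points in Group 1, 1/100 = 1.0 in Group 2, 1/150 = 0.67 in Group 3 and 1/75 = 1.33 in Group 4. How many children would be affected cannot be derived from the documents.

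**The case against.** **The SAP already contains a usable scale.** Its own table is complete, and that table's footnote ties grading at analysis to the intensity scale, most naturally the one printed there. An analyst working from the SAP may well use it. The SAP's references to the protocol are also loose: 4.4.1.1.2 cites Section 4.4.1.1.1 of the protocol, but that section is the SAP's own, and protocol Section 4 concerns ethics committees. The wording in 4.4.1.1.1 may be template text. This lowers the chance of harm, but the instruction and the table still disagree and the SAP does not say which governs.

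**The gap may be a PDF artefact.** A greater-than-or-equal sign can lose its bar when read from PDF, and this cannot be excluded. Against it, the strict sign stands at all four Grade 2 and Grade 3 lower bounds in both units, while the non-strict sign survives for Grade 1 in the same cell.

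**A reader might infer that boundary fevers will be dropped or set to None.** No section directs that. Coding 38.5 °C as None would contradict the definition row of the table being applied. It is one possible result of literal programming.

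**A reader might also put a percentage on the loss.** If excess over 38.0 °C falls off exponentially with mean m, in 0.1 °C steps and with r = exp(−0.1/m), the share of febrile readings at exactly 38.5 or 39.5 °C is (1 − r)(r^5 + r^15). This gives 5.5%, 7.6% and 8.1% for assumed m of 0.3, 0.5 and 0.8 °C. These are shares of readings under an invented distribution, whereas the endpoint is each child's maximum over several days. They do not estimate the effect on the reported results.

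**The consequence is limited.** Safety is an observational objective, summarised by group with confidence intervals and no test. The same rule applies to every group, and no comparative bias is shown.

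**Conclusion.** The point holds as a conflict between a stated derivation rule and the SAP's own table. As printed, protocol Table 9.2 does not grade 38.5 °C/101.3 °F or 39.5 °C/103.1 °F; the SAP table does, and SAP 5.7 is silent on the difference. Under the literal rule, a child peaking exactly on a boundary could be under-graded, or left out of the fever count if no other day is gradable.

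The size cannot be computed from the documents. It is probably small at subject level, because it needs a peak exactly on one of two values, and a child with another gradable febrile day still counts as having fever. The documents do not support a claim that fevers will be lost, or any particular rate of loss. The conclusion assumes that the printed inequality signs are faithful to the source. It is worth correcting because the ambiguity sits in a programmed safety endpoint and is cheap to remove.

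**What to change.** 1. In SAP 4.4.1.1.1, replace the reference to the protocol scales with the SAP's own solicited-reaction tables.
2. Correct those tables' numbers first: the list of tables and the introducing sentence say 4.1 and 4.2, while the captions say 4.3 and 4.4.
3. Repair the broken references in SAP 4.4.1.2.2 so that unsolicited fever uses the same scale, and correct the mistaken reference to the protocol in 4.4.1.1.2.
4. Add a line to SAP 5.7 stating that the Grade 2 and Grade 3 lower bounds for fever are inclusive, unlike protocol Table 9.2 as printed.

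This costs a few lines of SAP wording and a check that the fever-grading code matches. It needs no new data and no protocol amendment.

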4.4.1.1.2 Maximum Intensity

Maximum overall intensity is derived from the daily intensities computed as described in Section 4.4.1.1.1 of the protocol and is calculated as the maximum of the daily intensities over the period considered.

4.4.1.1.3 Presence

Presence is derived from the maximum overall intensity over the time period considered:

- None: No presence
- Grade 1, Grade 2, or Grade 3: Presence
- Missing or Unknown: Missing presence

Participants with at least one non-missing presence for a specific endpoint will be included in the analysis. Conversely, those without a non-missing presence will not be included in the analysis of the endpoint.

The time period is displayed as D0-D3, D4-D7, D8 and later.

4.4.1.1.4 Time of Onset

Time of onset is derived from the daily intensities computed as described in Section 4.4.1.1.1 It corresponds to the first day with intensity of Grade 1, Grade 2, or Grade 3.

Note: If a reaction is not continuous (i.e., reaction occurs over two separate periods of time intervened by at least one daily intensity Missing or None) then the time of onset is the first day of the first occurrence.

4.4.1.1.5 Number of Days of Occurrence During the Solicited Period

Number of days of occurrence over the period considered is derived from the daily intensities computed as described in Section 4.4.1.1.1. It corresponds to the number of days with daily intensities of Grade 1, Grade 2, or Grade 3. Number of days of occurrence on the solicited period with a specified intensity may also be derived.

4.4.1.1.6 Overall Number of Days of Occurrence

If a reaction is ongoing at the end of the solicited period, then the overall number of days of occurrence is derived from the daily intensities and the end date of the reaction after the end of the solicited period.

The overall number of days of presence is:

(End date – last vaccination date) + (number of days of occurrence within the solicited period) – length of the solicited period + 1

If the end date is missing or incomplete (contains missing data), the overall number of days of occurrence will be considered as Missing.

-
- Confidential/Proprietary Information
 - Page 48 of 67

4.4.1.1.7 Ongoing

Ongoing is derived from the last daily intensity of the solicited period computed as described in Section 4.4.1.1.1 and the maximum intensity on the ongoing period. The investigator's ongoing flag is not used because the measurement would determine the ongoing status of the reaction.

- Ongoing: if the last daily intensity of the solicited period is at least Grade 1 and the maximum intensity on the ongoing period is at least Grade 1
- Not ongoing: if the last daily intensity of the solicited period is None or the maximum intensity on the ongoing period is None.
- Missing: all other conditions (in this case, it is not included in the denominator of the ongoing analysis in the safety tables)

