4.3.2.3.1 Immediate Post-vaccination Observation Period

Subjects will be kept under observation for 30 minutes after each vaccination to ensure their safety. The post-vaccination observation should be documented in the source document. Any AE that occurs during this period will be noted on the source document and recorded in the CRB, as follows:

- Unsolicited systemic AEs will be recorded as immediate AEs in the CRB (presence marked as “yes” and details collected).
- Solicited and unsolicited injection site reactions and solicited systemic reactions will be recorded in the CRB in the same way as any reactions starting on the day of vaccination.
- SAEs will be recorded in the CRB and reported to the Sponsor in the same way as any other SAEs.

4.3.2.3.2 Reactogenicity (Solicited Reactions from Day 0 to Day 7 After Each Meningococcal Vaccination)

After the first vaccination, subject’s parents / guardians will be provided with a diary card, a digital thermometer, and a flexible ruler, and will be instructed how to use them. The following items will be recorded by the subjects in the diary card on the day of vaccination and for the next 7 days (i.e., D0 to D7) until resolution:

- Daily temperature, with the route by which it was taken
- Daily measurement or intensity grade of all other solicited injection site and systemic reactions
- Action taken for each event (e.g., medication)

The action(s) taken by the parent or guardian to treat and/or manage any **solicited reactions** will be classified in the CRB using the following list (all applicable items should be checked):

- None
- Medication
- Health care provider contact
- Hospitalized
- Discontinuation of study vaccination
- Whether the AE was related to the investigational product (for injection site events linked to routine pediatric vaccines)

The Investigator will assess the causal relationship between the AE and the investigational product as either “Not related” or “Related”.

Subject’s parents / guardians will be contacted by telephone 8 days after vaccination visit, to remind them to record all safety information in the diary card.

If the timing of the telephone call should fall on a weekend or a holiday, the call should be made on the next business day. If contact is not made on the designated day, study staff will continue calling until contact is made. Every telephone attempt and its outcome will be documented in the source document.

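### SAP 4.4.1.1.7 drops reactions still graded on D7 with no later record from the ongoing denominator, which biases the ongoing percentage upward, usually slightly

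*SAP*

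**What the plan says.** SAP 4.4.1.1.7 defines three classes from two inputs, the last daily intensity of the solicited period (D7) and the maximum intensity on the period after it.

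- Ongoing requires D7 at Grade 1 or higher and, in addition, that "the maximum intensity on the ongoing period is at least Grade 1".
- The second class is defined as "Not ongoing: if the last daily intensity of the solicited period is None or the maximum intensity on the ongoing period is None".
- The third is "Missing: all other conditions (in this case, it is not included in the denominator of the ongoing analysis in the safety tables".

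The same section sets aside the investigator's own assessment: the "ongoing flag is not used because the measurement would determine the ongoing status of the reaction".

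The post-D7 intensity has a single source. The note in SAP 4.4.1.1.1 says it is "derived from the record of the maximum intensity/measurement after the end of the solicited period". On what is recorded and for how long, SAP 4.3.2.3.2 (and Protocol 9.3.2.3.2) has the parents complete the diary "on the day of vaccination and for the next 7 days (i.e., D0 to D7) until resolution".

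**The concern.** The reason given for ignoring the flag is that the measurement decides. That reason fails where there is no measurement, and one such case is easy to foresee. If a reaction is graded on D7 and gone on D8, a parent who follows the diary instruction has nothing further to grade. The reaction is over, yet it cannot be classed as Not ongoing, because that needs None on D7 or a recorded None afterwards. It becomes Missing and is left out.

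The cases removed in this way are resolved reactions, so the remaining percentage overstates persistence. The number lost depends on how many reactions happen to end on D7. That could differ between vaccines, and the safety of Group 1 and Group 2 is described side by side.

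**Working it through.** The plan states no figure for this quantity, so there is none to reproduce. The check has two parts.

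**1. Enumerate the rule.** Each input can be None, Grade 1 or higher (G), or absent. Applying SAP 4.4.1.1.7 to all nine combinations:

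| D7 | After D7 | Class | In denominator |
|---|---|---|---|
| None | None, G or absent | Not ongoing | yes |
| G | None | Not ongoing | yes |
| G | G | Ongoing | yes |
| G | absent | Missing | no |
| absent | None | Not ongoing | yes |
| absent | G or absent | Missing | no |

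The row at issue is G on D7 with nothing after. No other rule changes it:

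- Step 1 of SAP 4.4.1.1.1 turns absent records into None only when CRF presence is No and every daily record is missing. It also excludes fever. A reaction graded on D7 cannot qualify.
- SAP 5.3.1 rules out replacing missing safety data.

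**2. Size the effect.** Notation and sources:

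- N = 200, the size of Group 1 (Protocol 6.5).
- q = share of children with the reaction on D7. Assumed, 2% to 20%.
- c = share of those whose reaction continues past D7. Assumed, 20% to 80%.
- Every child without the reaction on D7 has None on D7 and stays in the denominator.
- No reaction that ends on D7 has a later record.

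Formulas:

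- All children counted: Nqc / N = qc.
- Rule as written: Nqc / (N − Nq(1 − c)).
- Ratio of the second to the first: 1 / (1 − q(1 − c)), which does not depend on N.

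Worked case, q = 10% and c = 50%: 20 children have the reaction on D7, 10 continue and 10 end that day.

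- All counted: 10/200 = 5.00%.
- Rule as written: 10/(200 − 10) = 10/190 = 5.26%.
- Ratio: 1/(1 − 0.05) = 1.053.

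Ends of the assumed grid:

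- q = 2%, c = 80%: 1/(1 − 0.02 × 0.2) = 1/0.996 = 1.004.
- q = 20%, c = 20%: 1/(1 − 0.20 × 0.8) = 1/0.84 = 1.19 (4.00% becomes 4.76%).

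If the CRF does capture a post-D7 None for half of the reactions that end on D7, the worked case gives 10/(200 − 5) = 5.13%. If it captures one for all of them, the rate is 10/200 = 5.00% and the problem disappears.

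**The case against.** **The CRF may close the gap.** The documents do not show the CRF, and SAP 4.4.1.1.7 itself provides for a post-D7 maximum of None, so some such entries are evidently expected. This stands as a limit on how often the problem arises. It does not remove the problem, because nothing in the protocol or SAP requires that entry.

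**Setting the flag aside is deliberate.** SAP 4.4.1.1.1 notes that something the investigator calls a reaction may grade as None on measurement. That is a good reason to let a measurement override the flag. It is no reason to discard the flag when no measurement exists.

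**The bias could run either way.** A reaction that continued but lacks a post-D7 grade is also Missing, and losing it lowers the percentage. This is correct, but it needs a recording failure. The loss of reactions ending on D7 occurs even when the diary is kept exactly as instructed.

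**Stronger readings that a reader might infer.** Three are tempting, and the documents support none of them.

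- *The ongoing percentage is computed only among reactions that continued.* SAP 4.4.1.1.7 keeps every child with None on D7 as Not ongoing, and it does not restrict the denominator to reactions present on D7.
- *The late-period display has the same fault.* The sentence "The time period is displayed as D0-D3, D4-D7, D8 and later" belongs to Presence (SAP 4.4.1.1.3). Its inclusion condition is a non-missing presence for the endpoint, and no exclusion period by period is stated. The section could be more explicit, but it does not say that resolved reactions are removed.
- *Overall duration is lost for these reactions.* SAP 4.4.1.1.6 does not refer to the three classes of 4.4.1.1.7. The only condition it states for a Missing duration is a missing or incomplete end date.

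**Conclusion.** The point holds in a narrow form. A solicited reaction at Grade 1 or higher on D7 with no later intensity is classed as Missing and leaves the ongoing denominator, although the end date or the flag would often show whether it had stopped. For reactions that end on D7 the effect is an upward bias in the ongoing percentage.

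The size is small on the denominator that the section describes: a factor of 1.004 to 1.19 over the assumed range, and 5.3% against 5.0% in the worked case. These figures rest on assumed frequencies, on complete D7 data in the other children, and on the CRF not asking for a None entry after D7.

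The consequence is confined to descriptive safety tables. Ongoing status is not itself among the safety endpoints listed in SAP 4.3.2.2, the count of days within the solicited period (SAP 4.4.1.1.5) is unaffected, and no immunogenicity endpoint is touched. This is a minor correction, worth making because it costs so little.

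**What to change.** In SAP 4.4.1.1.7, keep the measurement rule wherever a post-D7 measurement exists, and add a fallback for D7 at Grade 1 or higher with no post-D7 intensity:

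- End date on or before D7, or ongoing flag No: Not ongoing.
- End date after D7, or ongoing flag Yes: Ongoing, with intensity missing.
- Neither field available: Missing, as now.

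The text should say which field takes precedence if the two disagree. The end date is the natural choice, since SAP 4.4.1.1.6 already uses it.

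At most, add one clarifying sentence to SAP 4.4.1.1.3: the display for D8 and later uses as its denominator the participants with non-missing presence for the endpoint.

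The cost is a few lines of SAP text and a small programming change. The SAP already refers to both fields, so no new data collection is needed.
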